4.1. Visit schedules

4.1.1. Phase I: First-line treatment

After eligibility has been evaluated and informed consent given for participation in the trial, patients will be randomized to receive oral methotrexate or mycophenolate mofetil. Patients will continue with this course of treatment unless treatment failure occurs due to safety, intolerability or lack of efficacy. If a failure is recorded within the first 6 months, the treatment assignment will be switched to the drug not initially randomized to, and the patient will follow a new visit schedule.

Patients who are treatment failures in Phase I due to safety (i.e. a serious adverse event deemed to be related to the study drug by the Medical Monitor) may or may not proceed to

Phase II depending on the Medical Monitor’s determination. In most cases of an SAE, the patient will likely not be allowed to switch to Phase II, but in some cases, such as an SAE due to intolerability, it may be deemed safe to switch to Phase II. Even if the patient does not switch to Phase II, outcome data at 6 months should be collected if the patient is willing.

Treatment success, according to the primary endpoint, will be assessed at 6 months. If treatment has been deemed successful for a patient at 6 months, they will be provided study medication for an additional 6 months and return for additional study visits as shown below. As long as the patient stays on the first randomized medication, Visit Schedule I will be followed.

Guidelines for Visit Schedule I

- Day 1 corresponds to the Baseline-I visit, which is also the first day the patient receives treatment.
- Visit windows are determined based on the date of randomization.
- The baseline eye exam and other baseline assessments may be collected at a separate visit up to 14 days before the patient is enrolled and randomized. Laboratory measurements may be collected within either 4 weeks or 90 days prior to the date of randomization, depending on the laboratory test.
- There should be a minimum of 2 weeks between each study visit.
- Data for the baseline and follow-up visits may be collected anytime within the visit window.

Table 9: Visit Schedule Phase I (0-6 months) or Phase II

Visit	Window Days/Weeks
Baseline*	
Week 2	±3 days
Month 1*	±15 days
Month 2	±15 days
Month 3	±15 days
Month 4	±15 days
Month 5	±15 days
Month 6	-15 to +30

*Every monthly visit scheduled will be calculated from the baseline visit date (Phase 1), using the average amount of days per month. If a patient does not come in within the visit window, every attempt should be made to get them in for a clinic visit as soon as possible.

Table 10: Visit Schedule Phase I (6-12 months)

Visit	Window (Weeks)
Month 9*	±15 days
Month 12*	-15 to +30

* Since baseline/treatment administration (Phase 1)

4.1.2. Phase II: Rescue treatment

In case of the first randomized treatment failure due to intolerability or lack of efficacy within the first six months of treatment, the treatment assignment will be switched to the alternate treatment. At this point, the patient will receive the antimetabolite not originally randomized to and will be followed an additional 6 months or until failure of the second treatment.

Patients will be given 2 weeks to enter into Phase II after treatment failure in Phase I. If patients do not enter within the 2-week window, they should be treated according to best medical judgment of their physician. If the physician believes a patient would benefit from treatment in Phase II, but there is an exceptional circumstance preventing the patient from entering Phase II within the 2-week window, contact the Coordinating Center for assistance.

Guidelines for Visit Schedule II

- Day 1 corresponds to the Baseline-II visit, which is also the first day the patient receives rescue treatment with the medication not initially received. Day 1 may be its own visit date (i.e. if within 2 weeks of the end of Phase I). Alternatively Day 1 may be the same day as the last day of Phase I. All study forms should indicate what visit it is for Phase I and what visit it is for Phase II, if applicable. See the following example below.

Phase	 1	 2								
Visit	 Baseline	 Two weeks	 Non-study visit (treatment failure only)							
Month:	 1	 2	 3	 4	 5	 6	 9	 12		

- Visit dates are determined based on the date of the Baseline-II visit (which may be the same date as Phase I treatment failure), and may not be changed.
- The Baseline-II visit form should be completed to gather information on any changes in health status or medications.
- There should be a minimum of 2 weeks between each study visit.
- Data for the follow-up visits may be collected anytime within the visit window.

4.1.3. Non-study visits

Despite the regular follow-up outlined in the visit schedules above, it is anticipated that some patients will have inflammation that is difficult to control or be intolerant to the drug, leading to additional visits. These additional visits may not fall within the study visit window. It is possible that the circumstances leading to such visits may result in changes to oral or topical corticosteroid dose, or a declaration of treatment failure and a need for rescue treatment. If treatment failure is declared at a non-study visit, all of the forms required at the time treatment failure is declared should be completed.

Guidelines for non-study visits

- Any changes to oral or topical corticosteroid dose will be noted on the appropriate form during the next scheduled study visit.
- If a treatment failure is declared at a non-study visit during follow-up while being treated during...
 - Phase I (initial randomized treatment): Record a treatment failure using Treatment Assessment Form. Perform Baseline II visit at this time or within 14 days. Phase II rescue treatment can start immediately.
 - Phase II: Record a treatment failure using the Treatment Assessment Form. Patient should continue to be followed until 6 months and 6th month data collected.
 - If treatment failure is declared at a non-study visit, an attempt should be made to collect as much information as possible, including the forms listed in Section 4.2.

4.2. Study form completion schedule

Forms	PHASE I					PHASE II				
	Baseline : Phase I	Week 2	Follow up months 1-5, 9	Treatment Failure anytime*	Follow up months 6 & 12	Baseline: Phase II**	Week 2	Follow up months 1-5	Treatment Failure anytime*	Follow up month 6
Eligibility/ Screening Form	X									
Consent Form	X									
Baseline History Form	X									
Clinical Eye Exam Form	X		X	X	X			X	X	X
Secondary Clinical Eye Exam Form	X			X	X				X	X
Visual Acuity Form	X		X	(x)	X			X	(x)	X
OCT Form	X		X	(x)	X			X	(x)	X
Fundus Form	X			(x)	X				(x)	X
Laboratory Report Form	X	X	X	(x)	X		X	X	(x)	X
Adverse Event Checklist		X	X	X	X	X	X	X	X	X
Vision Related Quality of Life	X			X	X				X	X
Health Related Quality of Life	X			X	X				X	X
Treatment Assessment Form	X	X	X	X	X	X	X	X	X	X
Patient Calendar***		X	X	X	X		X	X	X	X
Medication Log	X	X	X	X	X	X	X	X	X	X
Patient Dropout	(x)	(x)	(x)	(x)	(x)	(x)	(x)	(x)	(x)	(x)
Protocol Deviation Form	(x)	(x)	(x)	(x)	(x)	(x)	(x)	(x)	(x)	(x)
Adverse Event Narrative	(x)	(x)	(x)	(x)	(x)	(x)	(x)	(x)	(x)	(x)
Adverse Event Log	(x)	(x)	(x)	(x)	(x)	(x)	(x)	(x)	(x)	(x)

***Note that treatment failure may be declared at a scheduled study visit or at a non-study visit;**

All (x) are only to be filled out if applicable.

****If not switching on the same day as Phase I treatment failure**

*****Patients will complete this form and bring to the study coordinator for review**

4.3. Phase I Enrollment/Baseline visit

The Phase I Enrollment/Baseline visit should occur after the patient has been screened and determined to be eligible for the study. Screening is a process that should occur before or on the date of the patient's Enrollment/Baseline visit. The baseline eye exam and other baseline assessments may be collected at a separate visit up to 14 days before the patient is enrolled and randomized, with the exception of laboratory measurements which may be collected within 4 weeks or 90 days prior to or on the date of randomization (depending on the test).

Many patients will still have active enough inflammation at the time of enrollment to meet criteria ($\geq 1+$ AC cells, $\geq 1+$ vitreous haze by NEI scale, or active retinal/choroidal inflammation). However, some patients may have had active inflammation when screened (within 14 days prior to enrollment) but at the time of enrollment, the inflammation is improved because of steroid treatment. As long as the inflammation met inclusion criteria within this 14 day period, those values can be used for the baseline exam (enrollment exam). If there is a patient whom you think is very likely to be enrolled in the next 14 days but you are still waiting for some screening labs, it is fine to go ahead and consent and obtain the baseline study assessments (eye exam with secondary grader using both NEI and Miami scales for vitreous haze, fundus photos, OCT, questionnaires, etc.), as long as you do not randomize. Randomization can only occur once all eligibility criteria have been verified. The inflammation recorded on the baseline Clinical Eye Exam form needs to meet inflammation eligibility criteria.

4.3.1. Consent and eligibility evaluation

Procedures for obtaining consent include explaining the patient's disease, prognosis, and treatment options, discussing the risks and benefits of participation, and addressing the patient's questions and concerns. After explaining the nature of the study and the rights and responsibilities of the patient, the ophthalmologist and/or the study coordinator will obtain written consent from the subject, or written minor assent and parental consent if applicable. The subject is assured that participation in this study is voluntary and he/she can withdraw at any time if he/she feels uncomfortable.

The eligibility evaluation will be performed using the Eligibility Form, which is to be filled out at the Baseline-I visit. For detailed inclusion/exclusion criteria please see Section 2.3.

There is not a mandated separate visit for eligibility screening. If the patient fulfills all eligibility and exclusion criteria on a visit, he/she may sign the consent form and be randomized at the beginning of the official Baseline-I visit. Note that this requires that the patient have laboratory results that are current according to inclusion criteria guidelines.

In some cases, partial eligibility will be confirmed on a screening visit but more information may be needed (such as laboratory confirmation of acceptable values of the CBC, AST, ALT and creatinine). If and when the laboratory results meet eligibility criteria, the patient will then be asked to complete a consent form, followed by randomization and the official Baseline-I visit. All other criteria must be met at the time the consent form is signed and randomization occurs (except the active inflammation criteria which must be met within 14 days prior to randomization).

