2.4. Randomization and masking

Block randomization of the patients will ensure that an equal number of patients are randomized to each study arm at each site. Randomization lists will be created by the biostatistician ([REDACTED]) and accessed online via REDCap database. The following people will be able to access to the list of patients who have been randomized through the REDCap database:

Emergency Contact Personnel*

[REDACTED]

*Emergency contacts will log into REDCap to consult the list of randomized patients in case of an emergency in which unmasking is necessary for patient safety and [REDACTED] of the DCC cannot be reached.

Data Coordinating Center (DCC) Personnel

[REDACTED]

The study coordinators (listed below) will be aware of patient treatment assignment and will have a copy of the patient ID list for their site; however, they will not know future treatment assignments prior to randomizing patients. After consenting patients for enrollment and confirming all eligibility requirements have been met, study coordinators will log into REDCap and perform the randomization. Study coordinators will then give patients their assigned treatment.

The following study coordinators will have access to REDCap to perform randomizations but will not know the treatment assignments prior to randomizing patients:

[REDACTED]

[REDACTED]

[REDACTED] will act as study coordinator to [REDACTED] patients, as well as Coordinating Center Manager overseeing all other sites. [REDACTED] will have access to the randomization lists for other sites, in order to check patient treatment assignment as a quality assessment and manage distribution of medications to all sites.

All patients and study coordinators will be unmasked to treatment assignment after enrollment, as the two study drugs are different in appearance and must be administered on different weekly schedules. Study ophthalmologists performing the clinical eye exams, as well as visual acuity examiners, OCT operators, fundus photographers and fundus graders will be masked to treatment assignment to prevent bias in study outcomes. The [REDACTED] [REDACTED] investigational drugs department will purchase and supply mycophenolate mofetil and methotrexate.

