3.3. Study procedures

Enrollment/Baseline visit

Study coordinators should adhere to the following protocol for study procedures taking place at the enrollment visit.

- The patient's eligibility for participating in the study will be determined by the study ophthalmologist, aided by the study coordinator.
- If eligible, the patient will review the consent form with the study coordinator and the study physician, and give their consent.
- After consent, the study coordinator will assign the patient a unique Patient ID (derived from the list provided to study coordinator by the principal statistician).
- The study coordinator will then contact the designated person on site, holding the randomization list, to obtain the patient's drug assignment. This will be done away from sight of the study physician.
- The study coordinator will then label the medication with the assigned Patient ID. They should also place the appropriate number for the bottles (i.e. if it is the first bottle dispensed, it should have the #1 on the bottle).

Study visits

Study coordinators should adhere to the following protocol for study procedures taking place, after the patient is consented, enrolled and randomized. All study procedures should follow the schedule listed below:

- The patient comes for a study visit and meets with the study coordinator before their study doctor.
- The patient's medication bottle and folic acid bottle (*if applicable*) is immediately placed in a secure, opaque bag and left at the study coordinators desk for the remainder of the visit. Patient medication calendars should also be placed in the opaque bag.
- The study coordinator will check-in with the patient and complete the following in any order:
 - Review of patient medication diaries
 - Review of adverse events since last visit*
 - Dispense new medication bottle (*if applicable*)
 - Completion of SF-36 questionnaire (All patients) (*if applicable*)

- Completion of NEI-VFQ-25 (all patients) and IND-VFQ (Indian patients only)
- Remind the patient that they should not speak to their study doctor about their dosing schedule, or the name of the medication that they are currently taking.

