4.3.2. Randomization

Randomization treatment assignment takes place during the Baseline-I visit after eligibility has been determined and the consent forms have been signed by the patient. In some cases randomization can occur on the same day that patient is screened for enrollment, if the patient signs the consent form on that day. If the patient wishes to come back at a later time to sign the consent forms, randomization will occur on the date they return. If a patient returns to sign the consent and enroll on a different date to his or her screening visit, he or she must have had the relevant laboratory tests within 4 weeks prior to enrollment for trial eligibility.

After obtaining the written consent, the study coordinator will assign the next identification number from the patient ID list. The coordinator will then log into the REDCap database to perform the randomization for the corresponding patient ID. The coordinator will take note of the treatment assigned by REDCap, dispense the assigned treatment to the patient, and review dosing instructions with the patient.

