Because of the possibility that the outcome variable (BSCVA change score) will exhibit non-normality, we will repeat the analyses using transformations of the outcome data (including power and log transformations, or more general monotone transformations).

Additional analyses will be performed using age, gender, ethnicity, and the steroid dose at each month as predictors.

An additional supplemental analysis will be conducted using final BSCVA (instead of the change score) as the outcome, and including baseline BSCVA in each eye as a predictor, using methods otherwise identical to those above.

5. *Quality of life.* We will also use a linear mixed model to assess health-related quality of life, measured by the SF-36 questionnaire (PCS and MCS scores) and vision related quality of life NEI-VFQ-25 and IND-VFQ at 6 months or at the time of failure, as described in the Manual

of Operations. Predictors will be baseline quality of life, age, gender, ethnicity, study site (as a random effect), and treatment assignment, and we will test the hypothesis that the regression coefficient corresponding to treatment assignment equals zero using the Wald t-test. Similar assessments will be performed for vision-related quality of life questionnaires.

6. *Reason for discontinuation.* Individuals who discontinue study medication may do so due to inability to tolerate side effects, due to lack of efficacy, or for safety reasons. The outcome variable is whether the person discontinued due to intolerance, discontinued due to lack of efficacy, discontinued due to safety, or did not discontinue the medication. Because study site may be an important factor, we will use polytomous regression to model the discontinuation result as a function of treatment assignment (using a fixed effect for study site).⁷ If evidence is found that treatment assignment influences discontinuation result, further analyses may be conducted to determine whether or not treatment assignment is associated with discontinuation due to intolerance, lack of efficacy, or to safety, or some combination of these. We propose to classify all individuals in a two by four table according to treatment assignment and discontinuation (not discontinued, discontinued due to intolerance, discontinued due to lack of efficacy, discontinued due to safety) and conduct the Fisher's exact test (in its $r \times c$ form). The use of an overall test prior to further analysis is designed to protect the overall error rate.

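### Same-day enrolment can put the baseline questionnaires and acuity after the patient has learned the drug, and the plan does not require them to come first

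*Combined protocol and SAP*

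**What the plan says.** Protocol section 4.3.1 gives two routes into the trial. A patient who meets all criteria at a visit: "he/she may sign the consent form and be randomized at the beginning of the official Baseline-I visit". A patient who was waiting for laboratory results gives consent once they are acceptable, "followed by randomization and the official Baseline-I visit".

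Section 4.3.2 goes from consent to the ID number, the REDCap assignment and the medication. The coordinator is to "dispense the assigned treatment to the patient, and review dosing instructions with the patient". Section 2.4 confirms that the patient then knows the drug: "All patients and study coordinators will be unmasked to treatment assignment after enrollment". The required baseline procedures, including both kinds of questionnaire, are listed in section 4.3.3 with no statement of when they occur relative to randomisation. Section 5.1 likewise ties the questionnaires to the baseline visit only.

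Section 4.3 permits baseline assessments at a separate visit up to 14 days before randomisation. It names questionnaires among the items that may be collected early while laboratory results are pending.

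In SAP section 3.2.2, Planned Secondary Analyses, item 5 (quality of life) states: "Predictors will be baseline quality of life, age, gender, ethnicity, study site (as a random effect), and treatment assignment". Item 4 analyses best spectacle-corrected visual acuity as the change from baseline in each eye.

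**The concern.** A baseline covariate is safe to adjust for because treatment assignment cannot have influenced it. That guarantee is lost if the patient answers the questionnaire after being handed one of two recognisably different drugs. If knowing the drug moves the answers differently in the two arms, the model treats the difference as a pre-treatment imbalance and subtracts part of it from the treatment effect. A change score subtracts all of it.

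The questionnaires are the most exposed items because they are self-reported. Acuity is less exposed. The examiner is masked, but the result depends partly on the effort of a patient who is not.

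Earlier collection is optional, so some patients will have a baseline from before assignment and others may have one from after it. At stake are the quality-of-life comparisons and, to a lesser degree, acuity change.

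**Working it through.** **Order of events.** On the route where everything is done in one visit, sections 4.3.1 and 4.3.2 put consent, randomisation and dispensing at the start. Nothing in sections 3.3, 4.3, 4.3.3, 4.3.5 or 5.1 places the questionnaires or the acuity test ahead of that step. On the pending-laboratory route, section 4.3.1 puts randomisation ahead of the Baseline-I visit, while section 4.3 allows the same kind of patient to complete the assessments first. Both orders are therefore allowed.

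**Inputs from SAP section 3.4.2, item 4 (quality of life).** SD 8.4 points; baseline to 6-month correlation 0.6; adjusted SD 6.72; detectable difference 2.57 points at about 80% power. There are 108 patients per arm (section 3.4.1). Two-sided alpha of 0.05 is assumed, since item 4 does not restate it.

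**The SAP's own figure.**
- Adjusted SD = 8.4 × √(1 − 0.6²) = 8.4 × 0.8 = 6.72.
- Standard error of the contrast = 6.72 × √(2/108) = 0.914.
- Power for 2.57 points = Φ(2.57/0.914 − 1.96) = 0.802. The t-test version gives 0.799, and a detectable difference of 2.574.

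The stated 80% and 2.57 are reproduced. They use 108 per arm with no allowance for loss.

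**Bias from a shift at baseline.** Let d be the between-arm difference in the shift caused by knowing the drug, and f the share of patients whose baseline follows assignment. Neither is in the documents. Suppose the shift affects only the baseline score and the SDs are equal at the two times. The slope on baseline is then 0.6, and the adjusted contrast is biased by about 0.6 × f × d, in the direction opposite to the shift. The range tried is d from 0.5 to 2 points and f from 0.25 to 1. Only the product f × d matters.

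| f × d | Bias (points) | Power for 2.57 if the bias opposes the effect | Type I error |
|---|---|---|---|
| 0 | 0 | 80.2% | 5.0% |
| 0.125 | 0.075 | 77.9% | 5.1% |
| 0.25 | 0.15 | 75.4% | 5.3% |
| 0.5 | 0.30 | 69.9% | 6.2% |
| 1 | 0.60 | 57.7% | 10.1% |
| 2 | 1.20 | 32.2% | 25.9% |

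Example: f = 0.5 and d = 1 give 0.6 × 0.5 × 1 = 0.30. Power is then Φ((2.57 − 0.30)/0.914 − 1.96) = 0.70.

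**Acuity.** For a change score the slope is 1, so the bias is f × d letters. The comparison figure in SAP section 3.4.2, item 3, is a detectable 2.63 letters. The documents give no basis for a value of d here.

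**The case against.** Several points on the other side stand.

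- **Eligibility examination.** A reader might infer that the eye examination also follows randomisation, so that a patient whose inflammation falls short could be randomised. The documents do not support this. Section 4.3 requires all eligibility criteria to be verified before randomisation and adds: "The inflammation recorded on the baseline Clinical Eye Exam form needs to meet inflammation eligibility criteria". Section 4.3.1 requires the inflammation criteria to be met in the 14 days before randomisation. The grading must already exist.
- **Section 3.3.** A reader might take the sequence containing the SF-36 and NEI-VFQ-25 as proof that baseline questionnaires come second, because it covers "study procedures taking place, after the patient is consented, enrolled and randomized". That sequence largely describes follow-up visits: diaries, adverse events since the previous visit, returned bottles. The separate enrolment list in 3.3 does not mention questionnaires at all. The section leaves the order open.
- **Masking.** Ophthalmologists, acuity examiners, OCT operators, photographers and graders are masked (section 2.4). There is no evident route from the patient's knowledge to OCT or photographic grades. Coordinators who read questions aloud may not reword them (section 5.1). None of this protects answers given by the patient.
- **A check is already planned.** SAP section 3.2.2 repeats every secondary analysis with treatment as the only predictor. With the 6-month quality-of-life score as outcome (item 5), that repeat contains no baseline and cannot carry this bias. It is supplementary, however. It gives no protection for acuity change, nor for quality of life if the outcome is taken as change, as the variable list in SAP section 3.2.1 has it.
- **Size.** Both arms receive an active drug, and no document shows a differential shift. If the shift persisted to 6 months, the net bias for a fully affected group would be d − 0.6d = 0.4d, in the direction of the shift, against d with a pre-assignment baseline. Even the sign depends on assumptions.

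The permission to collect early does not answer the point. It is optional and does not govern same-day enrolment.

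**Conclusion.** The point holds in a limited form. The protocol allows, and in section 4.3.1 describes, randomisation and disclosure of the drug before baseline assessments that depend on the patient, and it never requires the reverse order. The baseline questionnaires, and to a lesser extent acuity, may be recorded after the patient knows the drug. It would go too far to say that they always are: the share affected is not given and could be small.

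Under the stated assumptions the quality-of-life bias runs from 0.075 to 1.2 points against a detectable 2.57, and is zero if there is no shift. These figures illustrate sensitivity; they do not estimate what happened. The conclusion about the order of events rests on the text alone and needs none of them.

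The primary outcome is not affected. Its planned model for 6-month success contains no baseline quality-of-life or acuity term, and the inflammation that qualifies a patient is verified before randomisation. This is a correction worth making to secondary outcomes, and it does not threaten the trial's main conclusion.

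**What to change.** In protocol sections 3.3, 4.3.1 and 4.3.2, state that randomisation takes place after all baseline assessments are complete, in particular the questionnaires and visual acuity. This replaces randomisation at the start of Baseline-I, and also the pending-laboratory wording that puts randomisation ahead of that visit. Have the coordinator confirm completion on the paper form before opening the randomisation. A confirmation on paper fits the existing workflow. A real-time REDCap block would not, because forms are completed on paper, scanned within 10 days and entered centrally (section 7.3).

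For patients already enrolled, add a sensitivity analysis of quality of life limited to those whose baseline questionnaires are dated before the day of randomisation. That restriction uses a fact fixed before assignment, so it keeps the randomised comparison and costs only precision. Dates cannot recover the order within one day, so all same-day baselines drop out. Read the result beside the planned repeat without covariates, with the 6-month score rather than the change as outcome.

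The cost is a slightly later randomisation within the same visit, one line on a form and one extra analysis. No visit or procedure is added. Table 1 lists enrolment and follow-up through April 2017, so the reordering may reach few new patients; for the rest the sensitivity analysis is the useful part.
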